5.10 Duration of Therapy and Criteria for Removal from Protocol Therapy

Participants will receive protocol therapy until one of the below criteria are met:

- Disease progression
- **Note:** Following consultation with the Study PI, participants who meet progression per 2014 Lugano classification⁸ but who meet the criteria of “indeterminate response” (IR) according to the provisional modification to the 2014 Lugano Classification, the LYRIC criteria¹⁰ ([Appendix C](#)), and are deriving clinical benefit may continue to receive protocol therapy beyond progression as long as they meet the following criteria:
 - Continue to meet treatment criteria
 - Investigator-assessed clinical benefit
 - Tolerance of study drug
 - Stable performance status
 - Treatment beyond progression will not delay an imminent intervention to prevent serious complications of disease progression (e.g., CNS metastases)
- *If the patient has IR per LYRIC criteria and is receiving therapy beyond progression:*
 - A confirmatory PET-CT should be performed within 12 weeks after initial progression to determine whether the patient meets PD criteria according to the LYRIC criteria¹⁰.
 - Further progression is defined according to the LYRIC criteria
 - Protocol therapy should be discontinued permanently upon documentation of PD per the LYRIC criteria
- Unacceptable toxicity despite dose delay/ modification

- **Note:** If one agent is delayed due to toxicity, then participants may continue with monotherapy for the other agent.
- Completed protocol therapy.
- General or specific changes in the participant's condition (including intercurrent illness) which render the participant unacceptable for further treatment in the judgment of the investigator
- Withdrawal of consent for further protocol therapy by the participant (See Section 16.5)

Once participants meet criteria for removal from protocol therapy, the participant should then proceed to End of Protocol Therapy assessments and follow-up.

Documentation of the reason for discontinuing protocol therapy and the date effective should be made in the medical record and appropriate eCRF. The COH DCC and the Study PI should be promptly notified of the change in participant status.

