11.0 ENDPOINT EVALUATION CRITERIA/MEASUREMENT OF EFFECT

11.1 Response/Progression

Disease response/progression will be evaluated using 2014 Lugano Classification (see [Appendix B](#))^{8,11}. Participants who meet the definition of progressive disease per Lugano Classification should be evaluated using the LYRIC criteria¹⁰ (see [Appendix C](#)). The ORR and CR rate will also be estimated according to the International Harmonization Project response criteria (Cheson 2007).⁹

PET-CT or diagnostic quality CT of the neck, chest, abdomen, and pelvis (N/C/A/P) with IV contrast will be performed at baseline (within the screening window, 28 days) prior to initiation of study therapy, and then after initiation of study therapy during cycle 4 and every 4 cycles thereafter until disease progression or off study therapy. Refer to [study calendar \(footnote r\)](#) for disease staging at EOT. Disease staging will be by either PET/CT (preferred) or CT scan, but, in patients with FDG-avid disease, it will be preferred (but not mandatory) to have PET/CT at baseline, Cycle 4 and at least every 8 cycles thereafter. In patients with FDG-avid disease, CR must be confirmed with PET/CT. Patients who enter CR with study therapy can be monitored with diagnostic quality CT scans thereafter until disease progression. MRI may be performed at the investigator's discretion for lesions not well-visualized by CT, or if CT with intravenous contrast is contraindicated. PET-CT and CT results will be read by radiology at each study site and investigator response based on radiology reading will be performed. Lymphoma response assessment based on PET-CT/CT will be based on the 2014 Lugano Classification ([Appendix B](#)).^{8,11}

Note: if there is no evidence of neck involvement by lymphoma at baseline, CT of chest, abdomen and pelvis (C/A/P) can be performed instead of N/C/A/P at subsequent re-staging.

Following initial screening, and unless clinically indicated, bone marrow specimens will be collected only to confirm CR.

For patients with progression of disease on imaging, it is strongly recommended that a confirmatory biopsy (performed as standard of care) be obtained whenever possible. Note that only an FDG-negative PET scan will be considered complete remission in patients whose tumor was FDG-avid at baseline.

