11.2 Clinical Endpoint Definitions

Overall Response Rate (ORR): Defined as the proportion of patients that have a documented CR or PR at any time during study treatment.

Complete Response (CR) rate: Defined as the proportion of patients that have a documented CR at any time during study treatment.

Duration of Response (DOR): Defined as the time from the first achievement of PR or CR to time of PD. Patients who never achieve PR or CR are excluded. Patient who has not had disease progression/relapse at last follow-up is censored at the time of last follow-up.

Overall Survival (OS): Defined as time from initiation of study therapy to death from any cause. If a patient is alive at the last evaluation time period, survival time is censored at the time of last follow-up.

Progression-Free Survival (PFS): Defined as the time from initiation of study therapy to the first observation of disease relapse/progression or death from any cause, whichever occurs first. If the patient has not progressed relapsed or died, the patient is censored at the time of last follow-up.

Toxicity: Toxicity and adverse events will be recorded using the NCI CTCAE 5.0 scale. Observed toxicities will be summarized by type (organ affected or laboratory determination such as absolute neutrophil

count), severity (by NCI CTCAE v5.0 and nadir or maximum values for lab measures), date of onset, duration, reversibility, and attribution.

Unacceptable Toxicity: defined as one of the following AEs that is at least possibly related to study treatment:

- Any **≥ grade 3 immune-related AE (IrAE)** that does not resolve to grade ≤ 1 within 7 days with the exception of:
 - Grade 3 immune-related hepatitis if ALT or AST < 8 x ULN or total bilirubin < 5 x ULN.
 - Grade 3 asymptomatic endocrinopathy.
 - Inflammatory response attributed to local antitumor response.
 - Vitiligo or alopecia of any grade.
- Any non-hematologic **grade 4 AE** that does not resolve to grade ≤ 1 within 7 days with the exception of:
 - Grade 4 asymptomatic lipase or amylase without evidence of pancreatitis
 - Grade 4 asymptomatic laboratory abnormalities including, but not limited to, hypo- or hyperglycemia, hypo- or hypernatremia, hypo- or hyperkalemia, hypo- or hypermagnesemia, hypo- or hyperphosphatemia, or hyperuricemia that do improve within 48 hours to Grade ≤ 2 with supportive measures.
 - Inflammatory response attributed to local antitumor response.
- Any Grade 5 AE.

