12.1.2 Phase 2 Design

In the phase 2 portion, patients will be treated at the RP2D. The phase 2 portion of this study will implement a Gehan two-stage design⁸⁸ to estimate the ORR and to evaluate the activity of the combination therapy. Patients treated during the Phase 1 portion at the RP2D will be included in the Phase 2 evaluations if they are evaluable for response, defined as patients who received at least 1 dose of pembrolizumab and at least 1 dose of pralatrexate and had at least 1 disease assessment ([Section 5.7](#)). The sample size is based on the desire to estimate the response rate with approximately 10% standard error, and early stopping if the combination is unexpectedly ineffective. In the pivotal PROPEL trial, the overall response rate (ORR) in 109 evaluable patients who received pralatrexate as a single agent was 29%, including 12 (11%) complete responses (CR) and 20 (18%) partial responses (PR).⁵

The phase 2 portion of the study is expected to evaluate a minimum of 7 and a maximum of 24 patients, including the patients treated at RP2D during the Phase 1 portion that are evaluable for response. At stage 1, if 0 responses are seen in the first 7 evaluable patients (including up to 6 patients enrolled during the Phase 1 portion that are evaluable for response), the study will be terminated and the true ORR will be declared $\leq 35\%$. If at least 1 patient responds, the trial will continue to the second stage. At stage 2, a total of 24 patients will be evaluated (including up to 6 patients enrolled during the Phase 1 portion that are evaluable for response).

This design provides for estimation of the response rate with approximately 10% standard error. The standard error will be 9.4%-10.2% after 24 patients if the ORR rate is 30%-70%. The maximum width of the 95% exact binomial confidence interval for ORR will be 42% after 24 patients. Under this design if the ORR is $>35\%$, there would be $\geq 95\%$ chance of at least one response among the first 7 patients.

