12.3.3 Analysis of Anti-tumor Activity

This study will aim to obtain an estimate of the anti-tumor activity of the study combination. ORR will be calculated as the proportion of evaluable patients that have confirmed CR or PR, as defined according to the 2014 Lugano Classification, exact 95% confidence intervals will be calculated for these estimates. Response rates will also be evaluated based on number and type of prior therapy(ies). Duration of response, as well as progression-free survival and overall survival will be estimated using the product-limit method of Kaplan and Meier. As secondary endpoints, the ORR and CR rate will also be estimated according to the International Harmonization Project response criteria (Cheson 2007).⁹

Any patient treated at the RP2D, including those from the Phase 1 portion, will be included in efficacy analyses. Patients will be evaluable for efficacy assessment if they received at least one dose of pralatrexate and at least one dose of pembrolizumab and underwent at least one response assessment. As discussed in [Section 5.7](#), patients will be evaluable for efficacy if they discontinued study therapy prior to the first response assessment because of progression of disease rather than solely because of unacceptable toxicity, withdrawal of consent, or investigator's decision.

12.3.4 Safety Analysis and Stopping Rules for Excessive Toxicity or for Rapid Disease Progression

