APPENDIX C: LYRIC CRITERIA

Lugano Classification was developed based on treatment with cytotoxic agents⁸. Immunotherapeutic drugs, may produce antitumor effects by potentiating endogenous cancer-specific immune responses. The response patterns seen with such an approach may extend beyond the typical time course of responses seen with cytotoxic agents, and can manifest as clinical responses after initial increases in tumor burden or even the appearance of new lesions. Thus, the 2014 Lugano Classification may not provide an accurate assessment of response to immunotherapeutic agents. Provisional modification of the Lugano criteria (LYRIC Criteria) may be used to assess participants who meet progressive disease per Lugano Classification^{8,10}.

Complete Response	Partial Response	Progressive Disease
Same as Lugano	Same as Lugano	
As with Lugano with the following exceptions:
 
Indeterminate response (IR)
 
 IR1: ≥50% increase in SPD of up to 6 measurable lesions in first 12 weeks of therapy without clinical deterioration IR2: <50% increase in the overall SPD with 
 a. Appearance of a new lesion(s), or b. ≥50% increase in PPD of a lesion or set of lesions at any time during treatment IR(3): Increase in FDG uptake without a concomitant increase in lesion size or number 
Patients with IR should continue on therapy and have repeat imaging after an additional 12 weeks (or sooner if clinically indicated).
 
Progressive disease criteria in these patients will be met if:
 
 IR1: An additional increase in the target SPD of ≥ 10% between the first IR1 timepoint and the SPD being assessed; or an increase in ≥ 5mm in either dimension of at least one lesion for lesions ≤ 2cm and 10mm for lesions > 2cm. IR2: the new or growing lesion(s) should be added to the target lesions (total of no more than 6) and there is PD if the SPD if the newly defined set of target lesions has increased ≥50% from their nadir value (which may precede the IR time point). IR3: There is evidence of PD by an increase in lesion size or the development of new lesions.

Abbreviations: SPD, sum of the product of the diameters; PPD, product of the perpendicular diameters.

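### The primary ORR is worded differently in 11.2 and 12.3.3, and neither section stops counting responses at Lugano progression although treatment may continue past it

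*Combined protocol and SAP*

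**What the plan says.** ORR per Lugano is a primary endpoint. It is described in three places.

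- Section 11.2, the endpoint definition: "Defined as the proportion of patients that have a documented CR or PR at any time during study treatment".
- Section 12.3.3, the analysis: "ORR will be calculated as the proportion of evaluable patients that have confirmed CR or PR, as defined according to the 2014 Lugano Classification". No time window is given here.
- Section 12.1.2, the stage-1 rule: the study is terminated "if 0 responses are seen in the first 7 evaluable patients". The rule refers to neither of the other two.

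The CR rate in 11.2 has the same on-treatment window: "Defined as the proportion of patients that have a documented CR at any time during study treatment". DOR is "Defined as the time from the first achievement of PR or CR to time of PD". PFS in 11.2 ends at the first observed relapse or progression, or at death.

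On confirmation, Section 11.1 says "In patients with FDG-avid disease, CR must be confirmed with PET/CT" and has bone marrow taken to confirm CR. It sets no such step for PR.

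On treatment after progression, Section 5.10 provides that patients who meet Lugano progression but have a LYRIC indeterminate response and "are deriving clinical benefit may continue to receive protocol therapy beyond progression", after consultation with the study PI and subject to listed conditions. Appendix C has such patients continue and be re-imaged. It explains that responses to immunotherapy "can manifest as clinical responses after initial increases in tumor burden or even the appearance of new lesions".

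**The concern.** Two things need settling before the primary endpoint is counted.

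The first is the word *confirmed* in 12.3.3. It has no counterpart in 11.2 and no procedure behind it for PR.

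The second, and more important, is that neither ORR text ends the count at Lugano progression. The protocol deliberately keeps some patients on therapy after that point because later shrinkage is possible. If it occurs on treatment, the literal definition in 11.2 makes the patient a Lugano responder. Under the same criteria the patient has already progressed for PFS. For DOR, one progression precedes the response and another may follow it, and the definition does not say which is meant.

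ORR is also the only input to the stage-1 stopping rule, and response is investigator-assessed in an open-label trial. The counting rule should therefore give one consistent answer before responses are known.

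**Working it through.** **1. The plan's own figures (12.1.2).** All three reproduce.

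- Standard error at n=24, √(p(1−p)/24): √(0.30×0.70/24) = 9.35% at p=0.30 (the same at 0.70), and √(0.50×0.50/24) = 10.21% at p=0.50. The plan states 9.4%–10.2%.
- Widest exact (Clopper-Pearson) 95% interval at n=24: 12/24, 29.1% to 70.9%, width 41.8%. The plan states 42%.
- Chance of at least one response in 7 at ORR 35%: 1 − 0.65⁷ = 95.1%. The plan states at least 95%.

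The question is which patients are counted, not the design arithmetic.

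**2. The definitions side by side.**

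| Element | 11.2 | 12.3.3 | 12.1.2, stage 1 |
|---|---|---|---|
| Qualifier | documented | confirmed | seen |
| Window | on study treatment | not repeated | not repeated |
| Denominator | patients | evaluable patients | evaluable patients |
| Cut-off at Lugano progression | none | none | none |

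The denominator is not in dispute, since both statistical sections use evaluable patients. In Appendix B the PR criteria are applied at a single assessment, with no repeat scan or interval.

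**3. One patient followed through the text.**

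- An on-treatment scan meets Lugano progression. This is a PFS event under 11.2.
- The finding also qualifies as a LYRIC indeterminate response, and the conditions of 5.10 are met. The patient stays on therapy and is re-imaged.
- A later on-treatment scan meets Lugano PR. Appendix C leaves the CR and PR criteria the same as Lugano.
- The scan lies within study treatment, so 11.2 counts a response. Nothing in 12.3.3 or 12.1.2 removes it. A CR would also enter the CR rate.
- DOR starts at this PR. The first Lugano progression lies before the start, and the text does not say that a later one is meant.

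**4. Size.** The documents give no basis for the number of such patients.

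- One patient: 1/24 = 4.2 points. For example, 8/24 = 33.3% (exact 95% CI 15.6–55.3%) against 9/24 = 37.5% (18.8–59.4%).
- Assuming 0 to 2 of 24 are affected: 0 to 2/24 = 0 to 8.3 points, below the planned standard error of 9.4–10.2 points.
- Stage 1: the rule separates 0/7 from 1/7 or more. A disputed patient changes the decision only if all six others are non-responders.

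**The case against.** The strongest reply is that 11.2 is the endpoint definition and 12.3.3 only says how the proportion is calculated, so the window need not be repeated. That stands. A reader might infer that the two sections conflict on the window, or that responses first seen after treatment stops are left open. The documents do not support this, because 11.2 already excludes them.

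It is also fair that *confirmed* most naturally means that the Lugano criteria are met, since the same sentence goes on to cite them. A reader might infer a repeat-scan requirement for PR, but no method or interval for one appears anywhere. This part is largely editorial.

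Three further inferences go too far.

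- *DOR cannot be computed for a post-progression responder.* Its definition does not specify the first progression, so a later progression could end it, or the patient could be censored. The endpoint is ambiguous, not incalculable.
- *The first scan always falls within the 12-week limit of the IR1 category.* With exact 21-day cycles, C4D1 is day 1 + 3×21 = 64, so D15–D21 is days 78–84. Section 5.2 allows 21 ± 3 days per cycle. With three 24-day cycles C4D1 is day 1 + 3×24 = 73, and D15–D21 is days 87–93. The point does not need this timing, since IR2 as written may occur at any time during treatment.
- *The chance of exactly one responder in seven measures the stage-1 risk.* It does not, because most sole responders would be ordinary ones with no earlier progression.

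Finally, the affected group is narrow: an indeterminate response, PI consultation, continuing benefit, and then a Lugano PR, which on CT means at least a 50% decrease in SPD with no new lesions. That limits the size. It does not remove the inconsistency with PFS, which follows from the stated rules.

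**Conclusion.** The concern holds in limited form and should be fixed. The primary ORR carries two qualifiers, one of which has no procedure for PR. Followed literally, it also counts a Lugano response after Lugano progression in a patient who already has a PFS event under the same criteria. The missing cut-off is common to 11.2 and 12.3.3; it is not a conflict between them.

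The effect is probably small: 4.2 points per patient at n=24, and 0 to 8.3 points on the assumption of 0 to 2 such patients. The stage-1 decision is affected only through a sole responder. The stated standard error, interval width and stage-1 probability are unaffected. The conclusion rests on the literal wording of 11.2 and on 5.10 being used as written; it does not question the rule on treatment past progression.

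**What to change.** Use one definition in 11.2, 12.1.2 and 12.3.3: best Lugano response of CR or PR among evaluable patients (as defined in 12.3.3), documented during study treatment and on or before the first Lugano progression or the start of new anticancer therapy, whichever of these limits comes earliest. Apply the same rule to the CR rate.

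Delete *confirmed* from 12.3.3 and keep the PET/CT and marrow requirements for CR in 11.1. If the sponsor does intend repeat-scan confirmation of PR, the method and interval must be stated instead.

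Report on-treatment responses first seen after Lugano progression only in the LYRIC secondary analysis; 12.1 already lists LYRIC response status among the secondary endpoints. With that cut-off, every counted response precedes the first Lugano progression, so DOR has a single end point.

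The on-treatment window of 11.2 is kept. Responses first seen after treatment stops therefore remain excluded unless the sponsor deliberately decides otherwise. A cut-off at progression or new therapy alone would drop that window without saying so.

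The cost is a wording change in three sections, with no new visits, scans or patients. The downside is that ORR may be slightly lower if a post-progression response occurs.

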5.3 Treatment Plan

For a tabular view of the treatment, monitoring, and follow-up schedule, see study calendar in [Section 10](#).

This is a phase 1/2 study, including a phase 1 dose-escalation portion of the study with 2 dose levels and 1 possible de-escalation dose level, for a total of 3 possible dose levels. The starting dose will be 20 mg/m² of pralatrexate on days 1 and 8 and 200 mg IV of pembrolizumab every 21 days, administered in 21-day cycles. The planned dose levels in the Phase 1 portion of the study are outlined in the table below.

Table 5.3 Dosing regimen and schedule

Dose level	Pembrolizumab (Day1)	Pralatrexate (Days 1 and 8)
-1	200 mg IV	15 mg/m ² IV
1	200 mg IV	20 mg/m ² IV
2	200 mg IV	30 mg/m ² IV

In the phase 2 portion of the study, subjects will receive therapy at the RP2D.

Intrapatient dose escalation is permitted in patients enrolled to dose level 1 if and only if the study proceeds to dose level 2 and dose level 2 is determined to be the RP2D. In that case, once dose level 2 is deemed safe and the study proceeds to the phase 2 portion of the study, patients who were enrolled to dose level 1 and are continuing to receive therapy can escalate to dose level 2 in their subsequent cycle of therapy. Patients must meet the criteria for initiation of subsequent cycles of therapy detailed in [Section 5.4](#) of the protocol.

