5.7 Replacement of Subjects

During the Phase 1 portion of the study, subjects will be replaced for any of the following:

- Missed any doses of pralatrexate during the DLT period (not due to DLT).
- Did not receive the doses of pembrolizumab during the DLT period (not due to DLT).

Subjects who are replaced for missed doses may continue to receive study treatment if there is clear clinical benefit, but will not be included in DLT analysis.

During the Phase 2 portion of the study, subjects who did not receive at least 1 dose of pembrolizumab and 1 dose of pralatrexate, or who did not have a tumor response assessment (except due to progression of disease prior to the first tumor response assessment) will be replaced. If a patient discontinues study treatment prior to the first response assessment due to progressive disease, the treating physician is encouraged to obtain imaging to confirm progression.

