12.1.1 Phase 1 design

During the Phase 1 portion of the study, a modified, more conservative version of the Rolling 6 design of Skolnik et al will be employed.⁸⁷ In this design, at most, 3 patients will be under observation for DLT on the current test dose level at any time. DLT observation period is 2 cycles (defined in [Section 5.5](#)). DLTs are defined in [Section 5.5](#). Patients who are not evaluable for DLT (defined in [Section 5.7](#)), i.e., those who did not receive the doses of pembrolizumab during DLT period (not due to DLT) or those who missed any doses of pralatrexate during DLT period (not due to DLT), will be replaced. Once 3 patients are evaluable

with no patient at that dose level experiencing a DLT, the dose can be escalated, or up to 3 additional patients may be treated at the current dose level. No more than 6 evaluable patients will be accrued to any dose level. Escalation will terminate as soon as ≥ 2 patients experience DLT at a given dose level. If 1/6 patients experience DLT at the current dose level, the dose will be escalated to the next higher level. If more than 1/6 patients experience DLT, then the next lower dose will be expanded. MTD will be declared the highest dose level at which 6 evaluable patients have been treated and, at most, 1/6 patients experience DLT. The MTD will be considered the RP2D, unless the PI chooses a lower dose level, based on toxicity in subsequent cycles.

These rules are outlined in the Table below.

Table 12.1.1. Dose Escalation Rules

# Patients on Current Level			Action
With DLT [^]	Evaluable	Evaluable + At Risk [^]	
0	0	1-2	Accrue next patient at this level*
0	0	3	Hold accrual
0	1	1-3	Accrue next patient at this level
0	1	4	Hold accrual
0	2	2-4	Accrue next patient at this level
0	2	5	Hold accrual
0	3-6	3-6	Accrue next patient at the next higher level* ^{*,+}
1	1	1-2	Accrue next patient at this level
1	1	3	Hold Accrual
1	2	2	Accrue next patient at this level
1	2	3-4	Hold accrual
1	3-5	3-5	Accrue next patient at this level
1	3-5	6	Hold accrual
1	6	6	Accrue next patient at the next higher level*
2**	any	any	Accrue next patient at next lower level (max 6)

[^]: DLT: a patient with a documented DLT

Evaluable: a patient who is either fully evaluable for toxicity for the purpose of dose escalations or has a DLT

At Risk: a patient who is on treatment and has not yet passed the evaluation period nor had a DLT

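### Section 12.3.3, read literally, puts dose-level-1 patients who later escalate to the RP2D into the RP2D efficacy set; Section 12.1.2 implies they are outside it

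*Combined protocol and SAP*

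**What the plan says.** Two sections define who enters the efficacy evaluation at the RP2D.

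- **Section 12.1.2 (design):** "Patients treated during the Phase 1 portion at the RP2D will be included in the Phase 2 evaluations if they are evaluable for response". It sets a maximum of 24 and qualifies both the stage 1 count and the total with "including up to 6 patients enrolled during the Phase 1 portion that are evaluable for response". The synopsis and Section 12.2 (12 + 18 = 30, with 6 shared) agree.
- **Section 12.3.3 (analysis):** "Any patient treated at the RP2D, including those from the Phase 1 portion, will be included in efficacy analyses". It then requires at least one dose of each drug and a response assessment (or early progression). It does not mention starting dose, assigned dose or a limit on the Phase 1 share.

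Section 5.3 plans a change of dose level. If level 2 is chosen as the RP2D and Phase 2 opens, "patients who were enrolled to dose level 1 and are continuing to receive therapy can escalate to dose level 2 in their subsequent cycle".

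Section 11.2 ties no endpoint to dose level. ORR is "Defined as the proportion of patients that have a documented CR or PR at any time during study treatment". OS is "Defined as time from initiation of study therapy to death from any cause", and PFS has the same starting point.

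**The concern.** A level-1 patient who escalates has been treated at the RP2D, but not during Phase 1. Section 12.3.3 therefore takes the patient in, while 12.1.2 does not. No passage says which section prevails, and none says how escalated patients are analysed.

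These patients are selected on a post-baseline outcome: they are still on therapy when Phase 2 opens. Level-1 patients who stopped earlier never enter. Under 11.2, a response reached at level 1 would count as an RP2D response, and survival before the first RP2D dose would count as RP2D survival. The primary objective is ORR at the RP2D. The selection pushes that estimate upward in expectation, though not in every data set, and the exact confidence interval does not reflect it. In an open-label single-arm trial, an unsettled population also leaves the choice open until responses are known.

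**Working it through.** **1. The plan's own figures (12.1.2) reproduce.** Stage 1: 1 − 0.65^7 = 0.951. Standard error: √(0.30 × 0.70/24) = 9.4% and √(0.50 × 0.50/24) = 10.2%. Maximum exact 95% interval width at n = 24: 41.8% (stated 42%). At the cited single-agent ORR of 29%, the standard error is √(0.29 × 0.71/24) = 9.3 points.

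**2. When escalation can happen.** The DLT period is 42 days (1.38 months).

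- *Planned accrual* (12.2): 30 to 36 patients in 48 months is 0.625 to 0.75 per month. With 3 or 6 patients at level 1 and 6 at level 2, level-1 patients reach the escalation point 9.4 to 19.0 months after C1D1. Example at 0.625 per month (one patient every 1.6 months) with 3 at level 1: the ninth patient starts at 8 × 1.6 = 12.8 months, and adding 1.38 gives 14.2. The three level-1 patients have then waited 14.2, 12.6 and 11.0 months.
- *Earliest case* (Table 12.1.1): level-1 starts on days 0, 1 and 2; patient 4 on day 42 and patient 5 on day 43, as places open; level 2 opens on day 44 with three evaluable patients and no DLT. At most "3 patients will be under observation for DLT on the current test dose level at any time", so six level-2 patients need 2 × 42 = 84 days, ending on day 128. Patients 4 and 5 have waited 86 and 85 days, about 12 weeks or 2.8 months.

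**3. How many remain (assumed model).** The documents give no time on therapy for the combination, so cited single-agent figures stand in for it: ORR 29%, median PFS 3.5 months, median remission 10.1 months. Responders respond at 2.8 months and then stay on therapy for an exponential time with median 10.1 months. Non-responders are exponential with median 2.1 months, solved so that the overall median is 3.5. Every remaining patient is assumed to escalate.

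P(responder and on therapy at t) = 0.29 × 2^(−(t − 2.8)/10.1)

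P(non-responder and on therapy at t) = 0.71 × 2^(−t/2.1)

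For waits of 14.2, 12.6 and 11.0 months, responders are 0.13 + 0.15 + 0.17 = 0.45 and non-responders 0.01 + 0.01 + 0.02 = 0.04, so about 0.48 patients remain (from unrounded terms).

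**4. Shift in expected ORR** if the k escalated patients (r of them responders) are added to 24: the mean of (X + r)/(24 + k) minus 0.29, with X ~ Bin(24, 0.29), by simulation (400,000 draws).

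| Accrual | Level-1 n | Remaining | Responders | Shift (points) |
|---|---|---|---|---|
| 0.625/month | 3 | 0.48 | 0.45 | +1.2 |
| 0.625/month | 6 | 0.81 | 0.77 | +2.1 |
| 0.75/month | 3 | 0.57 | 0.51 | +1.3 |
| 0.75/month | 6 | 0.97 | 0.89 | +2.4 |
| Groups of 3, back to back (18-24 weeks) | 3 | 1.34 | 0.79 | +1.6 |
| Groups of 3, back to back (18-24 weeks) | 6 | 2.40 | 1.51 | +3.0 |

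Hand check of the fourth row: (24 × 0.29 + 0.89)/24.97 = 7.85/24.97 = 31.4%, or +2.4.

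The earliest schedule in step 2 (waits of about 4.2, 4.2, 4.1, 2.8 and 2.8 months) stays in this range: 1.37 responders and 1.10 non-responders remain, and (6.96 + 1.37)/26.47 = 31.5%, or about +2.5.

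Varying the median remission over other values cited in the protocol (8.3 to 17 months) gives 1.0 to 3.4 points overall. At planned accrual, the chance that at least one level-1 patient remains is 41-66%, so the chance of none is 34-59%.

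**5. Single cases.** 7/24 = 29.2% becomes 8/25 = 32.0% with one escalated responder, or 7/25 = 28.0% with one escalated non-responder.

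**The case against.** The strongest answer is that the documents, read together, already settle membership. Section 12.1.2, the synopsis and Section 12.2 all give 24 with at most 6 from Phase 1. Escalation under 5.3 begins only after Phase 2 opens, so escalated patients were never treated at the RP2D during Phase 1. On this view the sentence in 12.3.3 is only a loose summary. That is probably the intent, and it is why the point is one of conflicting wording and not of a faulty design. But 12.3.3 is the section that governs the efficacy analyses. It states an inclusion rule, and nothing in it or elsewhere excludes these patients.

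It is also fair that the size rests on assumptions. The model borrows single-agent data, lets everyone escalate, and ignores the Section 5.4 criteria and stopping for toxicity or withdrawal. Denominators above 24 arise only on the literal reading.

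Three stronger readings are tempting and not supported:

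- A reader might infer that every escalated patient has been on therapy for at least 18 weeks (42 + 84 = 126 days) and so has already outlived the cited 3.5-month median PFS. Table 12.1.1 lets level 2 open while later level-1 patients are still at risk, so the wait can be about 12 weeks.
- A reader might infer that the rule of no responses in 7 is compromised. That rule sits in 12.1.2, which governs who counts there.
- A reader might infer bias from the missing limit of six in 12.3.3. Phase 1 patients replaced for DLT evaluation can still be response-evaluable, and under 5.7 "Subjects who are replaced for missed doses may continue to receive study treatment if there is clear clinical benefit", so the two sections may differ on them. But they started at the RP2D, and no bias is shown for them.

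**Conclusion.** The point holds for escalated patients. Sections 12.1.2 and 12.3.3 give different RP2D efficacy sets. The literal wording of 12.3.3 admits patients selected for still being on therapy and credits earlier responses and survival time to the RP2D. ORR, PFS and OS are then biased upward in expectation.

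The size is small: about 1 to 3 ORR points against a standard error of 9.3. It arises only if level 2 becomes the RP2D, some level-1 patients remain, meet the Section 5.4 criteria and escalate, and 12.3.3 is followed literally. The figures rest on the single-agent time-on-therapy model and on full escalation, so fewer escalations mean a smaller shift. No bias in PFS or OS has been quantified. The stated standard error, interval width and stage 1 probability are all correct. The correction is worth making because it fixes the primary-endpoint population in advance at almost no cost.

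**What to change.** Change the analysis set only; nothing about dosing or escalation changes.

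- In 12.3.3, with matching words in 12.1.2 and the synopsis, define the RP2D efficacy set as *response-evaluable patients whose first doses of pembrolizumab and pralatrexate were given at the RP2D*.
- Add that patients who reach the RP2D later by a change of dose level stay in their original dose-level group for ORR, CR rate, DOR, PFS and OS, are reported descriptively, and do not count toward the 24.
- As a minor wording point, make 12.1.2 and 12.3.3 agree on whether the limit of six applies to response-evaluable patients who started at the RP2D but were replaced for DLT evaluation.

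The cost is one or two sentences in each of three places. The first two changes need no extra patients or data, the total stays at 24, and the stated precision is unchanged. On the minor point, with 6 patients at level 1 and one such replaced patient, accrual is 6 + 7 + 17 = 30 if that patient counts or 6 + 7 + 18 = 31 if not, both within the maximum of 40.
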